#### 4. STUDY PLAN AND TIMING OF PROCEDURES

**Table 1 Study Plan – Enrollment, screening period**

Assessment/ activity	Refer to	Screening	
		V1 (W -2)	V1A d (V1 + max. 3 days)
Informed consent	10.4	X	
Inclusion/exclusion criteria	3.1/3.2	X	
Medical and asthma history	4.1.1	X	
Complete physical examination	5.2.1.1	X	
Weight, Height, BMI	5.3.1	X	
Vital Signs	5.2.2	X	
Local ECG	5.2.3	X	
Serum chemistry	5.2.4	X	
Hematology	5.2.4	X	
Urinalysis	5.2.4	X	
Blood concentration (digoxin, theophylline) a	3.5.2.2	X	
Serology (hepatitis B,C; HIV-1; HIV-2)	5.3.3.1	X	
Serum pregnancy test	5.2.4.1	X	
FSH b	5.2.4.1	X	
Adverse events	7.1	X	
Concomitant medication	3.5	X	
ACQ-6 at Study Center	5.3.2.1	X	
Pre- and post-bronchodilator spirometry c	5.1.1	X	X d
Review of the AI IFU and the Administration Questionnaire	6.6	X	
Training on epinephrine-containing device	3.5.1.2	X	

a If and when appropriate prior to treatment period; for patients who are on theophylline or digoxin, (see Section 3.5.2.2)

b FSH test done only for female patients to confirm postmenopausal status in women <50 years who have been amenorrheic for >12 month

c Pre- and post-bronchodilator spirometry can be done at Visit 1 ( or optional Visit 1Ad) OR Visit 2

d Visit 1A is optional for spirometry measurement only

**Table 2** Study Plan – Treatment period and follow-up

Assessment/ activity	Refer to	Treatment								EOT	IPD	FU	Unsch
		V2	V3	V4	V5	V6	V7	W16	W20				
		W0	W4	W8	W12	W28							
Visit window (days) a													
		±3	±3	±3	±3 h	±3 h	±3	±3	±3	±3	±3	±3	N/A
Adverse events	7.1	X	X	X	X	X	X	X	X	X	X	X	X
Concomitant medication	3.5	X	X	X	X	X	X	X	X	X	X	X	X
IP Administration at site g	6.6	X d	X e	X e									
IP Administration at home g	6.6				X e	X e							
Visit Reminder Call f	6.6				X	X							
Return of AI and admin. questionnaire	6.5				X	X							

a All visits are to be scheduled from the date of Visit 2 but not from the date of previous visit except in the case of early discontinuation from IP (see Section 3.6 for details).

b At those Visits training/review with the patient is optional.

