c For WOCBP only, a urine HCG test must be done prior to IP administration at Visits 2 (Week 0), 3 (Week 4), and 4 (Week 8) at the study center. At-home urine pregnancy tests are to be done by WOCBP prior to IP administration at Weeks 12 and 16 and repeated by the center staff at Visits 5 and 6. In the case of a positive test, the patient is NOT to administer IP and is to call the study center. Urine pregnancy tests will be done at the study center at the EOT visit (Visit 7, Week 20) and the Follow-up visit (Visit 8, Week 28).

d Study drug will be administered on site by HCP in either the arm, thigh, or abdomen

e At Visit 3, the patient/caregiver has the option to administer the study drug. At Visits 4, 5, and 6, the patient/caregiver must administer the study drug. If self-administered by the patient, the study drug can be given in the thigh or abdomen. If administered by the caregiver, the sites of injection are in the upper arm, thigh, or abdomen

f Study center to perform visit reminder call to the patient within 48 prior scheduled home administration date for V5 & V6

g In case of anaphylaxis, additional samples to be taken (see Section 6.7 and Appendix D)

h The±3 day window is related to the IP administration at home and not the clinic visit, which should occur no later than 48h after IP administration

i Pre- and post-bronchodilator spirometry can be done at Visit 1 (optional Visit 1A) OR Visit 2.

j Neutralizing antibody (nAb) testing will occur for all samples that are ADA positive. Samples that are ADA negative will not be tested for nAb.

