## **1.2 Study design**

This is an open-label study designed to assess patient- or caregiver-reported functionality, performance, and reliability of an AI with a fixed 30 mg dose of benralizumab administered SC in an at-home setting.

Approximately 120 patients, 18 to 75 years of age, globally with severe asthma will enter the treatment period to receive 5 SC doses (Week 0, Week 4, Week 8, Week 12, and Week 16) of benralizumab.

Following a 2-week screening period, eligible patients will receive 3 SC doses of 30 mg of benralizumab at the study site (Week 0, Week 4, and Week 8). At Week 0, the Principal Investigator (PI) or his/her designee will administer the study drug. At Week 4, the patient or caregiver will have the option of administering the study drug under site supervision to ensure they understand the procedure and are capable of doing so. At Week 8, the patient or caregiver will have to perform the injection, again under site staff supervision. Patients or caregivers unable or unwilling to administer investigational product (IP) at this visit will be discontinued from the study.

The patient or caregiver will be given the Instructions for Use (IFU) to refer to for home administrations. The final 2 doses of benralizumab (Week 12 and Week 16) will be self-administered by the patient or administered by the caregiver at home. After each of these administrations, the patient will return for a scheduled on-site visit within 48 hours.

For the at-home administrations, whether the patient is self-administering or the caregiver is administering to a patient, that person administering the dose will fill out a questionnaire designed to indicate whether the device functioned correctly and the dose was successfully administered. Both the completed questionnaire and the used device are to be returned to the site during each of the clinic visits (Visit 5 [Week 12] and Visit 6 [Week 16]). The site is to subsequently return the used devices and questionnaires to the Sponsor for evaluation.

An end-of-treatment (EOT) visit will be performed at Week 20 and a follow-up visit at Week 28 (12 weeks after last IP administration).

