### **3.3.1 Adverse events**

Adverse events (AEs) experienced by the patients will be collected throughout the entire study and will be coded using the latest version of the Medical Dictionary for Regulatory Activities (MedDRA) per the Data Management Plan.

Adverse event data will be categorized according to their onset date into the following study periods:

- AEs in the on-study period are defined as those with onset between day of the first dose of study treatment and scheduled follow-up visit, inclusive.
- AEs in the on-treatment period are defined as those with onset between day of first dose of study treatment and scheduled EOT for patients who complete study treatment or scheduled IPD visit for those patients who prematurely discontinue study treatment, inclusive. In the event that the EOT or IPD visit is beyond the protocol defined visit window, AEs with onset after the last dose of study treatment date+28 days+3 days (visit window) will be excluded from the on-treatment period and instead assigned to the post-treatment period.
- AEs in the post-treatment period are defined as those with onset after, but not including, the EOT visit (or the IPD visit) up to and including follow-up visit.

For instances where a patient attends the safety follow-up visit only, but does not attend an earlier IPD visit or EOT visit, AEs occurring on or after the day of the first dose of study treatment and on or before the last dose of study medication +28 days will be assigned to the on-treatment period, while AEs with onset date after this time will be assigned to the post-treatment period.

Adverse event on-study period is a combined period of on-treatment period and post-treatment period (when applicable).

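### The on-treatment adverse event period has three different end points, so an event about 23 to 34 days after the last dose can be on-treatment in one patient and post-treatment in another (minor)

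*SAP*

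**What the plan says.** SAP 3.3.1 gives the on-treatment period three possible ends.

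- **Visit attended in window.** The period runs from first dose to "scheduled EOT for patients who complete study treatment or scheduled IPD visit for those patients who prematurely discontinue study treatment, inclusive".
- **Visit beyond its window.** "AEs with onset after the last dose of study treatment date+28 days+3 days (visit window) will be excluded from the on-treatment period"; these events go to post-treatment instead.
- **Follow-up attended, but neither EOT nor IPD.** Events "on or before the last dose of study medication +28 days will be assigned to the on-treatment period". There is no 3-day allowance here.

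The post-treatment period is tied to the visit: "AEs in the post-treatment period are defined as those with onset after, but not including, the EOT visit (or the IPD visit"). It closes with the Follow-up visit. The on-study period is the two periods combined.

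Two footnotes to Protocol Table 2 fix the timing. Footnote a says "All visits are to be scheduled from the date of Visit 2 but not from the date of previous visit", except after early discontinuation. Footnote h says that for the home doses the ±3 "day window is related to the IP administration at home and not the clinic visit". Protocol 3.6 places the IPD visit 4 weeks ±3 days after the last administration.

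SAP 4.2.10.2 tabulates AEs for the on-study, on-treatment and post-treatment periods, summarises injection site reactions for the on-treatment period, and lists all AEs whatever the period.

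**The concern.** A period label in a safety table should depend on when the event happened relative to exposure. Here it also depends on the day the patient came to the clinic, and on whether the patient came at all. The SAP gives no reason for allowing 31 days when the visit is late and 28 when it is missed. Nor does an in-window visit mark a fixed time since the last dose, because the dose and the visit each move independently around days counted from Visit 2.

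At stake is how AEs are split between the on-treatment and post-treatment tables, and which injection site reactions enter a table restricted to the on-treatment period. The study is descriptive, so these counts are themselves the reported result.

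**Working it through.** **Inputs.** Scheduled study days are 113 for Week 16 and 141 for Week 20 (SAP 2.2.2, Table 1a). The windows are ±3 days on the Week 16 home injection and ±3 days on EOT (Protocol Table 2 and footnote h), both counted from Visit 2 (footnote a). IPD is 28 ±3 days after the last dose (Protocol 3.6). All cut-offs below are in days after the last dose.

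**Step 1: reproduce the SAP's figure.** 141 − 113 = 28, and 28 + 3 = 31. This matches the SAP's limit for a late visit. It allows for the visit window only and assumes the last dose was given exactly on Day 113.

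**Step 2: let both dates move.** The last dose can fall on Days 110 to 116 and an in-window EOT on Days 138 to 144.

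- Shortest gap: 138 − 116 = 22 days.
- Longest gap: 144 − 110 = 34 days.
- Of the 7 × 7 = 49 day pairs, 21 give less than 28 days, 7 give exactly 28 and 21 give more than 28. Six of the 49 exceed 31, and 37 lie between 25 and 31.

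These are counts of possible combinations, not expected frequencies.

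**Step 3: end of the on-treatment period by situation.**

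| Situation | End, days after last dose |
|---|---|
| EOT in window | +22 to +34 |
| IPD in window | +25 to +31 (28 − 3 to 28 + 3) |
| EOT or IPD late | capped at +31 |
| Follow-up only | +28 |

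**Step 4: the same event in different patients.**

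- *Onset at +33, last dose on Day 110.* With EOT on Day 144 the period ends at 144 − 110 = +34, so the event is on-treatment. With EOT on Day 145 the visit is late and the cap of +31 applies, so the event is post-treatment. Coming one day later shortens the period by 34 − 31 = 3 days.
- *Onset at +30.* On-treatment if EOT was at +31; post-treatment if EOT was at +28, or if only Follow-up was attended.
- *Onset at +26.* Post-treatment if EOT was at +25; on-treatment if EOT was missed and Follow-up attended.

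**Step 5: range affected.** With in-window, late or missed visits, onsets up to +22 are always on-treatment and onsets after +34 are always post-treatment. Only +23 to +34 can differ. Among patients who stop early (IPD in window, late or missed), the range is +26 to +31.

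**Step 6: the other reading of the text.** If the scheduled EOT means the planned Day 141 and not the visit held, the cut-off is 141 − 116 = +25 to 141 − 110 = +31. The spread narrows but does not disappear.

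**The case against.** The case for leaving the rule alone has four parts.

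*Ending at EOT follows the protocol.* The protocol describes a 20-week treatment period with EOT at Week 20, and Protocol 8.5.2 asks for AE counts by treatment and follow-up period. This stands as a reason for a visit-based cut. It does not explain why late and missed visits get different limits.

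*The spread is symmetric and mostly narrow.* A reader might infer from 21 of 49 pairs (43%) below 28 days that exposure time is systematically lost. The documents do not support that: another 21 pairs lie above 28, and 37 of 49 (76%) lie within 25 to 31. Nor do the six pairs above 31 break the SAP's limit, which applies only to visits beyond their window.

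*The late-visit rule does not contradict the post-treatment definition.* A reader might see a conflict, because events after +31 but before a late visit go to post-treatment, which is otherwise defined as starting after the visit. The late-visit sentence is an explicit exception and tells the programmer what to do.

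*Little depends on it.* There is one arm and no hypothesis test, so no comparison is biased. On-study tables and listings ignore the split. Completers have no dose left to discontinue after Week 16, so their counts of AEs causing discontinuation should hardly change. Injection site reactions could move only if they began more than three weeks after the last injection. All of this stands and limits the point to a minor one.

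A stronger inference is that patients who stop early lose most of a dosing interval. An IPD visit 7 days after the last dose would indeed put 28 − 7 = 21 of 28 days into post-treatment. But Protocol 3.6 sets that visit at 4 weeks ±3 days, so such a visit is a protocol deviation, and nothing in the documents suggests how often it would occur. An in-window IPD falls at most 3 days short of 28. What remains is that no SAP rule clearly corrects for a visit held well before its window.

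**Conclusion.** The point holds as a minor inconsistency. SAP 3.3.1 can classify AEs with the same onset time after the last dose differently because of visit dates, for onsets about 23 to 34 days after that dose. The result assumes that doses and visits are in window, late or missed as the documents define them, and that the period ends at the visit actually held; on the planned-date reading a smaller spread remains.

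The consequence is limited to a few descriptive counts in the on-treatment and post-treatment tables, including the on-treatment injection site table. The number of patients affected cannot be derived from the documents. A reader should not infer that the overall safety conclusion is unreliable: on-study summaries and listings are the same under any of these rules.

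A related gap is that the SAP gives no period rule for a patient who attends none of EOT, IPD and Follow-up.

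**What to change.** Use one cut-off anchored on the last dose for every patient, whichever visits were attended:

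- on-treatment: onset from the first dose date to the last dose date +31 days, inclusive, which is the SAP's own 28 + 3;
- post-treatment: later onset, up to and including the Follow-up visit.

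Keep the on-study definition ending at Follow-up so that the two periods still add up to it. This removes the spread between patients, and it makes the late-visit exception and the separate Follow-up-only paragraph unnecessary. It also gives a defined end to the on-treatment period when no later visit took place.

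If the visit-based cut is preferred, the minimum change is to use the same limit for late and missed visits and to say whether a scheduled visit means the planned date or the visit held.

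The cost is an SAP wording change and a simpler derivation, with no new data and no change to study conduct. Protocol 8.1 allows SAP amendments until database lock. The downside is that a few events around EOT change period and the cut no longer coincides exactly with the visit. At the extremes, 31 − 22 = 9 days after an early in-window EOT become on-treatment, and 34 − 31 = 3 days before a late in-window EOT become post-treatment.

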### **3.3.2 Laboratory variables**

Blood and urine samples for determination of clinical chemistry, hematology and urinalysis parameters will be taken at the times detailed in the CSP, and will be assessed in a central laboratory. The parameters outlined in Section 5.2.4, Table 3 of the CSP will be collected. Laboratory data is to be reported in SI units.

Changes in hematology and clinical chemistry variables between baseline and each subsequent assessment will be calculated. For values recorded with a leading greater than or less than (>, <) symbol, the reported numeric value will be used for analysis and the value with the symbol will be included in the listings, unless otherwise specified. For example, a value of <0.01 will be analyzed as 0.01 and listed as <0.01.

Absolute values will be compared to the relevant reference range and classified as low (below range), normal (within range or on limits) or high (above range). The central laboratory ranges will be used for laboratory variables. All absolute values falling outside the reference ranges will be flagged.

Urinalysis data will be categorized as negative (0), positive (+), or strongly positive (++, +++, or >+++) at each time point.

For the purposes of hematology, clinical chemistry and urinalysis shift tables, baseline will be defined as the latest non-missing assessment prior to first IP dose date, and maximum or minimum value post-baseline will be calculated over the entire post-baseline period, including the unscheduled assessments.

For the liver function tests: aspartate aminotransferase (AST), alanine aminotransferase (ALT), alkaline phosphatase, gamma-GT (GGT) and total bilirubin (TBL), the multiple of the central laboratory upper limit of the normal (ULN) range will be calculated for each data point.

$$\text{Multiple} = \text{Value} / \text{ULN}$$

For example, if the ALT value was 72 IU/L (ULN 36) then the multiple would be 2.

Patients who meet any of the following criteria at any point during the study will be flagged:

- AST  $\geq 3 \times \text{ULN}$
- ALT  $\geq 3 \times \text{ULN}$
- TBL  $\geq 2 \times \text{ULN}$

### 3.3.3 Vital signs

Pre-dose vital signs (pulse, systolic blood pressure, diastolic blood pressure, respiration rate, and body temperature) will be obtained in accordance with schedule provided in the protocol.

Changes in vital signs variables between baseline and each subsequent scheduled assessment will be calculated. Absolute values will be compared to the relevant reference ranges and classified as low (below range), normal (within range or on limits) or high (above range). All values (absolute and change) falling outside the reference ranges (see [Table 4](#)) will be flagged.

**Table 4** Vital signs reference ranges

Parameter	Standard Units	Lower Limit	Upper Limit
Diastolic Blood Pressure (DBP)	mmHg	60	120
Systolic Blood Pressure (SBP)	mmHg	100	160
Pulse Rate	Beats/min	40	120
Respiratory Rate	Breaths/min	8	28
Body Temperature	Celsius	36.5	38
Weight	kg	40	200

Body mass index (BMI) will be calculated from the height and weight as follows:

$$BMI (kg/m^2) = weight (kg) / (height (m))^2$$

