### **2.3 Baseline and change from baseline**

In general, the last non-missing observation prior to the first dose of study treatment will serve as the baseline measurement. If there is no value prior to the first dose of study treatment, then the baseline value will not be imputed and will be set to missing.

Unless indicated otherwise, Visit 2 (Week 0) is the planned baseline visit, for all assessments carried out at the center.

Change from baseline will be calculated as the post-baseline assessment value minus the baseline assessment value. If either value is missing, then the change from baseline value will be missing.

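### SAP 3.3.3 flags vital-sign changes from baseline against limits that exist only for absolute values, so nearly every change is flagged and the flag tells the reader nothing

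*SAP*

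**What the plan says.** SAP 3.3.3 sets three rules for vital signs.

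- Change: "Changes in vital signs variables between baseline and each subsequent scheduled assessment will be calculated". SAP 2.3 defines it: "Change from baseline will be calculated as the post-baseline assessment value minus the baseline assessment value". A patient whose reading does not move therefore has a change of 0.
- Classification into low, normal or high, which is worded for absolute values only. The sentence begins "Absolute values will be compared to the relevant reference ranges and classified as low (below range), normal (within range or on limits) or high (above" and ends by defining high as above the range.
- Flagging: "All values (absolute and change) falling outside the reference ranges" are to be flagged, with a reference to the table of vital-sign ranges in the same section.

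That table has four columns: parameter, unit, lower limit and upper limit. Typical rows are "Systolic Blood Pressure (SBP) mmHg 100 160" and "Pulse Rate Beats/min 40 120". There is no column for change. SAP 4.2.10.4, which lists the vital-sign outputs, gives no limits for change, and neither does any other part of the SAP or protocol.

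The matching laboratory rule in SAP 3.3.2 flags absolute values only.

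**The concern.** The flagging sentence applies one pair of limits to two quantities on different scales. An absolute pulse is centred somewhere inside 40 to 120; a change in pulse is centred near 0, which lies outside that range. A flag meant to pick out unusual values would then mark the ordinary ones.

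What is at stake is the usefulness of one safety display and fidelity to the plan. Protocol 8.5.2 leaves the definition of noteworthy laboratory values to the SAP and asks for similar summaries of vital signs, and SAP 3.3.3 is where the vital-sign limits are set. A programmer who follows the sentence produces change flags with no content. A programmer who sees the problem has to drop the rule or invent limits, and either is an undocumented departure from the SAP.

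**Working it through.** The plan states no figure on this point, so there is none to reproduce. The check applies the rule to the SAP's own table.

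**Inputs.** The limits L and U come from SAP 3.3.3, including "Diastolic Blood Pressure (DBP) mmHg 60 120" and "Respiratory Rate Breaths/min 8 28". Change d = post-baseline value minus baseline value (SAP 2.3).

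**Step 1: when does a change escape the flag?** Only when L ≤ d ≤ U. Every L is positive, so d = 0 and every d < 0 are flagged for every parameter. The smallest change that escapes is d = +L.

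**Step 2: can a change between two in-range readings escape?** The largest such rise is U − L. It must be at least L to escape.

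**Step 3: what share is flagged?** Taking d as Normal with mean 0 and standard deviation s, the share is 1 − [Φ(U/s) − Φ(L/s)]. The documents give no s, so the values below are assumptions shown as a range.

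| Parameter | L | U | Smallest unflagged change | Largest rise within range (U − L) | Assumed s | Share flagged |
|---|---|---|---|---|---|---|
| Diastolic pressure (mmHg) | 60 | 120 | +60 | 60 | 6, 10, 15 | 100%, 100%, 99.9968% |
| Systolic pressure (mmHg) | 100 | 160 | +100 | 60 | 8, 15, 20 | 100% for each |
| Pulse (beats/min) | 40 | 120 | +40 | 80 | 6, 10, 15 | 100%, 99.9968%, 99.617% |
| Respiratory rate (breaths/min) | 8 | 28 | +8 | 20 | 2, 3, 4 | 99.9968%, 99.617%, 97.725% |
| Temperature (C) | 36.5 | 38 | +36.5 | 1.5 | 0.3, 0.5, 0.8 | 100% for each |

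Entries of 100% are rounded to four decimals of a percent.

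Worked examples:

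- Respiratory rate, s = 4: 1 − [Φ(28/4) − Φ(8/4)] = 1 − [Φ(7) − Φ(2)] ≈ Φ(2) = 0.97725.
- Pulse, s = 15: 1 − [Φ(120/15) − Φ(40/15)] = 1 − [Φ(8) − Φ(2.667)] ≈ Φ(2.667) = 0.99617.

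**Step 4: direction.** For systolic pressure (60 < 100) and temperature (1.5 < 36.5), no change between two in-range readings can escape. For pulse, a change of 0 is flagged while a rise of 40 to 120 beats/min is not. The rule is only partly inverted, because large falls, and rises above U, are still flagged.

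**Weight.** The table also lists weight, 40 to 200 kg, so the same logic would flag any weight change below +40 kg. But protocol 5.3.1 ties weight to the screening schedule (protocol Table 1) alone, and SAP 3.3.3 does not name weight among the vital signs to be obtained. A weight change may therefore never arise, and weight is left out of the table above.

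**The case against.** The strongest reply is that this is a slip of wording with almost no consequence. Most of that stands.

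- The low/normal/high classification refers to absolute values, so the baseline-to-maximum and baseline-to-minimum shift tables in SAP 4.2.10.4 should be untouched. The descriptive statistics use no flag.
- No hypotheses are tested, and vital signs are not among the outcome measures listed for the safety objective. Vital-sign deteriorations that meet the seriousness criteria or lead to discontinuation of treatment are reported as adverse events by a separate route (protocol 7.3.6).
- The laboratory rule, and the sentence just before the flagging rule, both suggest that only absolute values were meant. A programmer may well read it that way.

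A reader might infer three stronger things that the documents do not support.

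- *That changes would be labelled abnormal.* The SAP says only that they are flagged; it does not apply its classification to changes.
- *That the change flags would bury true out-of-range readings in the listings.* That depends on a listing layout the SAP does not specify. SAP 4.2.10.4 promises a listing of recorded data, and a flag attached to a change would leave the flag on the absolute value readable.
- *That every change for every parameter would be flagged.* Respiratory-rate rises of 8 to 28 breaths/min escape, and weight changes may not occur.

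The reply does not cure the text. The sentence names change explicitly, and no limits exist to make that part of the rule meaningful. The table has four headers and four entries in each row, so there is no sign of a lost column.

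**Conclusion.** The rule is wrong as written, with small consequences. That zero and every decrease are flagged, and that only a rise of at least the lower limit escapes, follows from the SAP's own table and needs no assumption. The percentages rest on assumed standard deviations and a mean change of zero. Within the ranges tried, the lowest share flagged is 97.7%, for respiratory rate at a standard deviation of 4 breaths/min. Nearly all change values would be flagged, so the change flag has no practical use. The damage is confined to flags on changes in vital-sign outputs; the absolute flags, classification, shift tables, endpoints and confidence intervals stand.

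**What to change.** In the flagging sentence of SAP 3.3.3, delete the words *and change*, so that only absolute values are flagged against the table, as SAP 3.3.2 already does for laboratory data. If flags on changes are wanted, add separate, pre-specified limits for change for each parameter, for both rises and falls. The first option costs two words and no new data. The second needs the limits to be agreed and entered in the SAP before database lock. Neither alters any endpoint.
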